22.4.4 Additional Analyses of the Primary Efficacy Outcomes

Additional and sensitivity analyses of the primary efficacy outcomes (Early Clinical Response and Investigator's Assessment of Clinical Response at PTE) will be performed. Analyses for the FDA primary efficacy outcome will be described here and in more detail in the SAP. Analyses for the EMA primary efficacy outcome will be described in the SAP.

If the null hypothesis of inferiority is rejected for the Early Clinical Response in the mITT population and the observed success response proportion for omadacycline is larger than the observed proportion for linezolid, a formal statistical analysis of superiority will be conducted. If the lower limit of the 2-sided 95% CI for the treatment difference is greater than 0%, omadacycline will be considered superior to linezolid.

The primary efficacy outcome will be assessed separately across the stratification factors of type of infection and receipt of allowed antibacterial therapy in the 72 hours prior to randomization stratum by treatment group. For each type of infection stratum and each prior antibacterial therapy stratum, a 2-sided 95% CI for the observed difference in Early Clinical Response rates will be calculated for the mITT population. Additional subgroup analyses of the primary efficacy outcome may be conducted as descriptive analyses.

Sensitivity analyses include: conducting an adjusted analysis of the primary efficacy outcome based on the randomized stratum and separately, based on the stratum the subject actually belongs, and conducting an analysis where all subjects with an Indeterminate response are considered Clinical Successes.

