8.3 Handling of Missing Data

Missing data will be handled as outlined below:

- All missing and partial dates for adverse events or for medications received after randomization will be queried for a value. If no value can be obtained, substitutions will be made as detailed in [Appendix 3](#). These substitutions will be used in calculations; however, the actual value recorded on the eCRF will be used in all listings.
- Missing start and stop times for prior and concomitant antibiotics will be queried for a value. If no value can be obtained but the site indicates the antibiotic was received (onset time) prior to the first dose of test article, 00:01 will be used for the onset time. If the site also indicates that the end time was prior to the first dose of test article, 00:01 will be used for end time. The actual value (blank) will be recorded on the eCRF and will be used in the listings.
- Missing times for lesion measurements will be queried for a value. If minutes are not available, the time will be recorded to the closest hour.
- If the time of the outpatient dose of test article on Day 1 is missing, it will be imputed to 23:59.
- If no value can be obtained for all other times for events and assessments occurring after randomization, the time will not be imputed but will remain missing.
- The severity and causality assessment for adverse events cannot be missing. Missing data will be queried for a value.

For clinical and microbiological response, missing data will be handled as follows:

- For the primary outcome measure (Early Clinical Response at 48 to 72 hours):
 - The subject will be considered to have missing data if there is no lesion size measurement (either length or width) at either baseline or 46 to 72 hours after the first dose of test article. Subjects with missing data will be defined as an Indeterminate response which is essentially a Clinical Failure for the primary analysis (mITT and ITT populations).
 - If the time of administration of the first dose of test article is missing, the subject will be defined as an Indeterminate response which is essentially a Clinical Failure for the primary analysis (mITT and ITT populations).
- For the secondary outcome measures (investigator's assessment of Clinical Response at the EOT and PTE Visits):

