10 EFFICACY PARAMETERS

For all efficacy analyses, subjects will be analyzed in the group to which they were randomized. By definition, subjects who receive the wrong test article are not included in the CE-EOT, CE-PTE, ME-EOT and ME-PTE populations. Subjects who are randomized to the wrong infection type or prior antibiotic stratum will be analyzed in the stratum to which they were randomized, unless otherwise stated. A summary of the efficacy analyses is provided in [Appendix 2](#).

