10.1 Primary Analysis

The primary efficacy analyses will be based on the mITT population. The non-inferiority test will be a 1-sided hypothesis test performed at the 2.5% level of significance. This non-inferiority test will be based on the lower limit of the 2-sided 95% confidence interval (CI). The primary efficacy outcome is the percentage of subjects with an Early Clinical Success at 48 to 72 hours after the first dose of test article.

The number and percentage of subjects in each treatment group defined as an Early Clinical Success, Clinical Failure and Indeterminate (subjects with missing data or who are lost to follow-up) will be tabulated, as will the overall category combining Clinical Failure and Indeterminate. The null and alternative hypotheses are as follows:

$$H_0 : p_1 - p_2 \leq -\Delta \text{ and } H_1 : p_1 - p_2 > -\Delta ,$$

where p_1 is the primary efficacy outcome rate in the omadacycline treatment group, p_2 is the primary efficacy outcome rate in the linezolid treatment group, and Δ is the non-inferiority margin of 10%.

To test the null hypothesis, a 2-sided 95% CI for the observed difference in primary outcome rates (omadacycline treatment group minus linezolid treatment group) will be calculated for the mITT population. If the lower limit of the 95% CI for the difference in the mITT population exceeds -10% , then the null hypothesis will be rejected and the non-inferiority of omadacycline to linezolid will be declared.

The 2-sided 95% CI for non-inferiority testing based on the difference of Early Clinical Success rates at 48 to 72 hours after the first dose of test article, will be computed using the method proposed without stratification by Miettinen and Nurminen³. For notation purposes, assume 1 represents the omadacycline group (Group 1) and 2 represents the linezolid group (Group 2).

Based on Miettinen and Nurminen, the 2-sided 95% CI is given by the roots for $RD = p_1 - p_2$ of the following equation:

$$\chi^2_\alpha = \frac{(\hat{p}_1 - \hat{p}_2 - RD)^2}{V}$$

where χ^2_α is the cut point of size α from the chi-square distribution ($\chi^2_\alpha=3.84$ for 2-sided 95% CI); RD is the difference between the 2 true rates ($RD = p_1 - p_2$); \hat{p}_1 = the observed average proportion in Group 1; \hat{p}_2 = the observed average proportion in Group 2; and

$$V = \left[\frac{\tilde{p}_1(1-\tilde{p}_1)}{n_1} + \frac{\tilde{p}_2(1-\tilde{p}_2)}{n_2} \right] \frac{n_1 + n_2}{n_1 + n_2 - 1}$$

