10.2 Sensitivity and Additional Analyses of the Primary Efficacy Outcome

Sensitivity analyses of the primary outcome include:

- Determination of the 95% CI adjusted for infection type and receipt of prior antibiotics. If there are < 20 subjects within a stratum and treatment group, or there is a 0 count within a stratum for a treatment group and outcome, wound and abscess will be combined. If the combining of the infection types is not sufficient to complete the adjusted analysis, the prior antibiotic strata will be combined into one group. The 95% CI interval will be computed using the stratified methodology of Miettinen and Nurminen. Cochran-Mantel-Haenszel weights will be used for the stratum weights in the calculation of the CI as follows, where n_{1i} = number of subjects in Group 1 in the i th stratum; n_{2i} = number of subjects in Group 2 in the i th stratum:

$$W_i = \frac{n_{1i}n_{2i}}{n_{1i} + n_{2i}}$$

- The second sensitivity analysis of the primary outcome will consider all subjects who are lost to follow-up prior to a lesion size assessment from 46 to 72 hours or have missing data as an Early Clinical Success (these subjects are considered Indeterminates and analyzed as Clinical Failures in the primary analysis).
- A multiple imputation analysis using a Markov chain Monte Carlo full data imputation will be used to define missing data. Fifty data sets will be created using this technique in which type of infection (cellulitis/erysipelas, major cutaneous abscess and wound infection), prior receipt of antibiotics (yes and no), infection result of IV drug use, (yes and no) and baseline

lesion area ($\leq 300 \text{ cm}^2$, > 300 to 600 cm^2 , > 600 to 1000 cm^2 , and $> 1000 \text{ cm}^2$) are included as predictive variables.

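### The multiple-imputation sensitivity analysis leaves treatment arm out of the imputation model, so as written it shrinks the treatment difference toward zero by about the fraction missing

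*SAP*

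**What the plan says.** SAP 10.2 gives three sensitivity analyses of the primary outcome. The third reads: "A multiple imputation analysis using a Markov chain Monte Carlo full data imputation will be used to define missing data". The next sentence begins "Fifty data sets will be created using this technique in which type of infection (cellulitis/erysipelas, major cutaneous abscess and wound infection), prior receipt of antibiotics", continues with IV drug use and a four-level baseline lesion-area category, and ends by saying that these "are included as predictive variables". That is the whole specification. It does not mention treatment arm, the analysis applied to each completed data set, or the rule for combining the 50 results.

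No other section fills the gap:

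- SAP 10 states: "For all efficacy analyses, subjects will be analyzed in the group to which they were randomized". This fixes the arm in which a subject is counted. It says nothing about the model that generates missing outcomes.
- SAP 8.3 gives the primary rule: "Subjects with missing data will be defined as an Indeterminate response which is essentially a Clinical Failure for the primary analysis".
- Protocol 22.4.4 lists stratum-adjusted analyses and "conducting an analysis where all subjects with an Indeterminate response are considered Clinical Successes", but no multiple imputation. Protocol 22.15 describes none either.

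**The concern.** An imputation model should contain the variable whose effect is being estimated. If arm is absent, a missing omadacycline subject and a missing linezolid subject with the same baseline covariates are imputed from the same success probability. The imputed part of the data then carries no treatment difference and dilutes the difference seen among observed subjects.

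In a non-inferiority trial the direction matters. If omadacycline is truly worse, dilution moves the estimate and the lower limit away from -10, so the result looks better than the same imputation with arm included. If omadacycline is truly better, the advantage is understated.

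The usefulness of the analysis is also at stake. It is there to test whether the conclusion depends on counting missing as failure. If it returns nearly the same point estimate as that rule by construction, the agreement could be mistaken for robustness.

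**Working it through.** **Inputs.** From SAP 5.1.1 and 10.1: success rate 79% in both arms, margin 10 points, 1-sided alpha 0.025, 90% power, 704 subjects randomized 1:1 (352 per arm). From SAP 10.2: 50 imputed data sets. Assumed, because the documents give no figure: 2 to 15% of outcomes missing, completely at random; Rubin's rules for pooling.

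**The plan's own figure.** Farrington-Manning: n per arm = [(1.960·s0 + 1.282·s1)/0.10]². Here s1 = √(2 × 0.79 × 0.21) = 0.576, and s0 = 0.580 from the restricted estimates under the null. This gives 351.5, so 352 per arm and 704 in total, as stated. Power for the three planned comparisons is 90.0, 95.6 and 96.9%, against the stated 90, 96 and 97%.

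**Expected difference without arm.** Let p1 and p2 be the true rates, d = p1 − p2, and m1 and m2 the missing fractions. Ignoring covariates, which randomization balances, the common imputation rate is

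p* = [p1(1−m1) + p2(1−m2)] / (2−m1−m2).

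The expected difference is (1−m1)p1 + m1·p* − (1−m2)p2 − m2·p*, which reduces to

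d × [1 − (m1(1−m2) + m2(1−m1)) / (2−m1−m2)].

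With m1 = m2 = m this is d(1−m).

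Example with 69% versus 79% and 10% missing: p* = 0.74; omadacycline 0.9 × 0.69 + 0.1 × 0.74 = 0.695; linezolid 0.9 × 0.79 + 0.1 × 0.74 = 0.785; difference −0.090 instead of −0.100. With 5% missing in one arm and 10% in the other, the factor is 1 − 0.14/1.85 = 0.924, giving −9.24.

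**Simulation at the margin.** True rates 69% versus 79%, 352 per arm, beta-binomial imputation, 100,000 trials per row, both versions scored on the same trials:

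| Missing (omadacycline / linezolid) | Estimate, arm omitted | Estimate, arm included | Lower limit above −10, arm omitted | Lower limit above −10, arm included |
|---|---|---|---|---|
| 2% / 2% | −9.82 | −10.02 | 2.62% | 2.49% |
| 3% / 3% | −9.71 | −10.01 | 2.68% | 2.46% |
| 5% / 5% | −9.50 | −9.99 | 2.87% | 2.53% |
| 10% / 10% | −9.00 | −9.99 | 3.25% | 2.49% |
| 15% / 15% | −8.50 | −10.00 | 3.79% | 2.59% |
| 5% / 10% | −9.24 | −9.99 | 2.93% | 2.42% |
| 10% / 5% | −9.25 | −10.01 | 3.14% | 2.54% |

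The Monte Carlo standard error of each paired gap is 0.01 to 0.04 points. The mean lower limit at 5, 10 and 15% missing is −16.1, −15.8 and −15.4 without arm, against −16.6, −16.8 and −17.0 with it.

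**With the four listed covariates.** Multivariate-normal draws (one reading of the named MCMC method; covariate mix and effects assumed; 6,000 trials each) give −9.47, −9.05 and −8.47 without arm and −9.97, −10.06 and −9.97 with it, at 5, 10 and 15% missing. The listed predictors do not stand in for arm.

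**Other true differences** (20,000 trials each; 5, 10, 15% missing, arm omitted). A true −5 becomes −4.8, −4.5, −4.2. A true +5 becomes +4.8, +4.5, +4.2. Equal rates stay at 0.

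**The case against.** The strongest reply is that this shrinkage is not peculiar to the imputation. With equal missingness m, counting missing as failure gives (1−m)p1 − (1−m)p2 = (1−m)d, and counting missing as success gives the same. In the 69% versus 79% setting the chance that the lower limit clears −10 is:

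| Missing per arm | Missing = failure (primary) | Missing = success | Imputation, arm omitted | Imputation, arm included |
|---|---|---|---|---|
| 5% | 3.4% | 3.6% | 2.9% | 2.5% |
| 10% | 4.8% | 5.1% | 3.3% | 2.5% |
| 15% | 6.2% | 6.8% | 3.5% | 2.5% |

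(20,000 trials per row, a separate run from the one above; Miettinen-Nurminen limits for the two single-value rules.) So the arm-free imputation is not more lenient than the primary test. This stands, and the comparison made here is only with the same imputation including arm. The primary rule targets a composite in which missing is failure, so its excess over 2.5% is not a true type I error. The equality also shows the weakness: with equal missingness, all three treatments of missing data share one expected point estimate, and none recovers the difference among observed subjects.

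Second, the effect may be tiny. The endpoint falls at 48 to 72 hours, the odd-numbered Day 2 and Day 3 doses are to be taken at the site (Protocol 14.3.1.1), and the design assumes equal rates. Nothing in the documents points to 10 or 15% missing. This stands as a limit on size.

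Third, by-arm imputation may have been intended, in which case arm would be a grouping variable and would not appear among the predictors. That is possible, but the text does not say so, and a programmer following the list would produce the diluted version.

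**Conclusion.** The concern holds. SAP 10.2 neither includes treatment arm in the imputation model nor says imputation is by arm, and no other section does. Followed as written, the estimated difference is about (1 − fraction missing) times the difference that the same imputation would give with arm included.

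For a true −10 points the loss is 0.2 to 0.3 points at 2 to 3% missing and 0.5, 1.0 and 1.5 points at 5, 10 and 15%. The chance that the lower limit clears −10 rises by 0.1 to 0.2 points at 2 to 3% missing, and by about 0.3, 0.8 and 1.2 points at 5, 10 and 15%. These sizes rest on assumed missing rates, missingness completely at random, and Rubin pooling.

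The primary conclusion and the sample size are unaffected, and the SAP attaches no pass/fail rule to this analysis. It is worth correcting because the stated predictor list produces a diluted estimate and removes most of the value of the analysis as a check on the primary missing-data rule.

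**What to change.** Add to SAP 10.2, before unblinding, that imputation is run separately within each randomized treatment group (or that randomized group is in the imputation model), that the difference in Early Clinical Success rates is computed in each of the 50 data sets, and that the results are combined by Rubin's rules. Either option removes the dilution, but the SAP should name one so that the method is uniquely specified. It should also name the variance of the per-data-set difference, because Rubin's rules need a variance and the primary score interval does not supply one directly. If by-arm imputation was already intended, the same text records it.

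The cost is one or two sentences and about one line of code. The sensitivity interval becomes slightly less favourable. With true rates of 79% in both arms, the lower limit clears −10 in 88.7, 87.3 and 85.1% of trials with arm included, against 90.0, 89.4 and 89.9% without, at 5, 10 and 15% missing.

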10.3 Secondary Analysis

The number and percentage of subjects in each treatment group with a Clinical Success, Clinical Failure, and Indeterminate for the overall assessment of Clinical Response at the PTE Visit (based on the investigator's assessment) will be reported for the mITT and CE-PTE populations (by definition CE-PTE subjects cannot have a response of Indeterminate). Two-sided 95% CIs will be constructed for the observed differences in the Clinical Success rate using the method of Miettinen and Nurminen without stratification. The 95% CIs are for descriptive purposes only and no conclusion of NI will be made. The reasons for Clinical Failure will be summarized by treatment group.

The number and percentage of subjects in each treatment group in each response category for Early Clinical Response will be presented for the micro-mITT population. The number and percentage of subjects who are classified as a Clinical Success and Clinical Failure based on the overall assessment of Clinical Response at the PTE Visit (based on the investigator's assessment) in the ME-PTE population will be calculated. Two-sided 95% CI without stratification will be constructed for the observed difference in the Clinical Success rates using the method of Miettinen and Nurminen.

Early Clinical Response and the overall assessment of Clinical Response at the PTE Visit by baseline pathogen will be determined as the proportion of subjects with a Clinical Success, for each pathogen isolated at baseline for the blood culture or the culture of the ABSSI site. The number and percentage of subjects in each treatment group with a Clinical Success (based on Early Clinical Response and investigator's assessment of response) will be tabulated per pathogen for the micro-mITT and ME-PTE (for investigator's assessment only) populations. Early Clinical Response and the overall assessment of Clinical Response at the PTE Visit in the micro-mITT and ME populations will also be provided by mono-microbial and poly-microbial infections (Gram-positive only and mixed infections [Gram-positive and Gram-negative]).

10.4 Additional Analyses

Additional efficacy analyses will be conducted to support the efficacy findings of the primary and secondary outcomes. CIs will be determined for descriptive purposes, but no conclusions of NI will be made.

Clinical Outcomes

The number and percentage of subjects classified as an Early Clinical Success, Clinical Failure and Indeterminate at 48 to 72 hours after the first dose of test article in the ITT population will be calculated. A 2-sided 95% CI without stratification will be constructed for the observed difference in the Clinical Success rate using the method of Miettinen and Nurminen.

The number and percentage of subjects classified as a Clinical Success, Clinical Failure and Indeterminate by the investigator's assessment at EOT in the mITT and CE-EOT populations (by

definition subjects with an Indeterminate response are excluded from the CE-EOT population) will be calculated for each treatment group. A 2-sided 95% CI without stratification will be constructed for the observed difference in the clinical success rate using the method of Miettinen and Nurminen.

A summary (number and percentage of subjects) of the shift from baseline to each visit (Day 2, Day 3, Day 7, Day 10, EOT and PTE Visits) in the clinical signs and symptoms (presence of drainage, tenderness, edema, erythema, induration) of the ABSSSI will be presented by treatment group for the mITT and CE-PTE populations. The number and percentage of subjects with resolution of all clinical signs and symptoms that were present at baseline will be presented for each visit throughout the study. The assessment of the systemic signs will also be summarized at each time point these were measured. This includes descriptive statistics of the WBC count, temperature and immature neutrophils as continuous variables, percentage of subjects with a WBC count $\geq 10,000$ cells/mm³ or < 4000 cells/mm³, fever (defined as temperature $> 38^{\circ}\text{C}$), $> 15\%$ neutrophils, presence of lymphadenopathy proximal to primary lesion site and presence of lymphangitis proximal to the primary lesion site.

Descriptive statistics of the primary infection site measurements (surface area [length x width]) will also be provided at each visit the infection site was measured for the mITT populations. The measurement at the visit, the absolute change from baseline, and the percent change from baseline will be provided at each visit. The percent change from baseline will be categorized as, $< 0\%$ (any increase), and decreases of 0 to $< 5\%$, 5 to $< 10\%$, 10 to $< 15\%$, 15 to $< 20\%$, 20 to $< 30\%$, 30 to $< 40\%$, 40 to $< 50\%$ and 50% to 100%.

All-cause mortality (ACM) at 30 days after randomization will be summarized in the ITT population. Subjects who are lost to follow-up will be excluded from this analysis.

Descriptive statistics of temperature will be provided for each visit temperature was measured for the mITT and CE-PTE population. The measurement at the visit and the absolute change from baseline will be provided at each visit, as will the percentage of subjects who have a temperature $\leq 37.8^{\circ}\text{C}$.

A concordance analysis of the primary efficacy outcome (Early Clinical Response at 48 to 72 hours) with the overall assessment of Clinical Response at the PTE Visit (based on the investigator's assessment) and the investigator's assessment of Clinical Response at the EOT Visit will be conducted in the mITT population. A concordance analysis of per-subject microbiological response and the investigator's assessment of Clinical Response at the EOT Visit will be conducted in the micro-mITT population.

For the micro-mITT and ME populations, the number and percentage of subjects with an Early Clinical Success (only micro-mITT population), with an assessment of Clinical Success (based on the investigator's assessment) at the EOT Visit (micro-mITT and ME-EOT populations) and an overall assessment of Clinical Success at the PTE Visit (based on investigator's assessment, micro-mITT and ME-PTE populations), will be tabulated by baseline MIC to omadacycline and linezolid by pathogen (for those pathogens occurring at least 5 times in one of the treatment groups) and treatment group.

Microbiological Outcomes

The per-subject microbiological response at the EOT and PTE Visits in the micro-mITT, ME-EOT (EOT Visit only) and ME-PTE (PTE-Visit only) populations will be determined to support the clinical findings. The number and percentage of subjects classified with a favorable (eradication and presumed eradication) and unfavorable (persistence, presumed persistence, and indeterminate) microbiological response (by definition, indeterminates are excluded from the ME population) will be tabulated for both treatment groups. A 2-sided 95% CI without stratification will be constructed for the observed difference in the per-subject favorable microbiological response rate between the omadacycline and linezolid groups using the method of Miettinen and Nurminen.

Per-subject microbiological response at the PTE Visit in the micro-mITT and ME-PTE populations will also be provided by mono-microbial and poly-microbial infections (Gram-positive only and mixed infections [Gram-positive and Gram-negative]).

Microbiologic response by baseline pathogen will be determined as the proportion of subjects with a favorable microbiological response (eradication or presumed eradication) at the EOT and PTE Visits for each pathogen isolated at baseline from the blood culture or culture of the ABSSSI site. The number and percentage of subjects in each treatment group with a microbiologically favorable outcome will be tabulated for the micro-mITT, ME-EOT (EOT Visit) and ME-PTE (PTE Visit) populations. Favorable microbiologic response by baseline pathogen will also be summarized separately for pathogens obtained from the blood culture (ie, for bacteremic subjects) for the micro-mITT population.

Microbiological categories for pathogens identified after baseline assessment are superinfection and new infection. The number and percentage of subjects with a superinfection or new infection will be presented by treatment group. A listing will be provided that presents the subjects with a superinfection and new infection including the type of specimen and pathogen.

Decreasing susceptibility of a pathogen is defined as a 4-fold increase from baseline to any subsequent study time point in the MIC of the test article received. The number and percentage of subjects in the micro-mITT population with a pathogen showing decreasing susceptibility will be tabulated for each treatment group. In addition, a table will list all subjects in each treatment group with a pathogen showing decreasing susceptibility, including the type of specimen, pathogen, and MIC values. Additional exploratory microbiological analyses may be conducted.

Subject Reported Outcomes

At the Screening, Day 3, EOT and PTE visits the subject will complete a numerical rating scale for pain⁴ (average pain over the last 24 hours) at the primary ABSSSI lesion site. The numerical rating scale anchors will range from 0 to 10, where 0 represents “No pain” and 10 represents “Pain as bad as you can imagine.” Descriptive statistics of the numerical rating scale for pain at each time point and the change from baseline for each time point will be provided by treatment group for the mITT population.

At the Screening and PTE visits the subject will complete a SF-36v2[®] Health Survey (Medical Outcomes Trust, Optum[™]). The SF-36v2[®] Health Survey asks 36 questions to measure functional health and well-being from the subject's point of view. The SF-36v2[®] Health Survey consists of 8 scaled scores (vitality, physical functioning, bodily pain, general health perceptions, physical role functioning, emotional role functioning, social role functioning, and mental health) which are weighted sums of the questions in their section. Each scale is transformed into a 0 to 100 scale with the lower the score the more disability. There are 2 composite scores: physical and mental. Descriptive statistics for the composite scores and each subscale will be provided for baseline, the PTE visit and the change from baseline by treatment group for the mITT population.

Subject reported outcomes will be analyzed independently from other data collected in the study.

